10.3.2 Pharmacokinetic Statistical Methodology

All PK parameters will be summarized by treatment using descriptive statistics.

The PK parameter estimates will be evaluated to delineate dose proportionality. Log-transformed C_{max} , and AUC(0- ∞) of LY3819253 will be evaluated using a power model (where log-dose acts as an explanatory variable) to estimate ratios of dose-normalized geometric means and corresponding 90% confidence intervals. Results of the dose proportionality analysis will be plotted.

The estimated ratio of dose-normalized geometric means of PK parameters between the highest and lowest doses will be used to assess dose proportionality.

Example SAS code for the analysis:

```
proc mixed data=pk;
model log_pk = log_dose / alpha=0.1 cl solution residual ddfm=kr2;
estimate '700 mg' intercept 1 log_dose 2.87506126 / alpha=0.1 cl; /*Log of 700 */
estimate '2800 mg' intercept 1 log_dose 3.44715803 / alpha=0.1 cl; /*Log of 2800 */
estimate '7000 mg' intercept 1 log_dose 3.84509804 / alpha=0.1 cl; /*Log of 7000 */
estimate '2800 mg - 250 mg' log_dose 0.97003679 / alpha=0.1 cl; /*Difference in
log values of 7000 and 700 */
ods output solutionf=est;
ods output estimates=estims;
run;
```

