4.3. Justification for Dose

The dose levels selected for this study are designed to explore a wide exposure-response range that potentially encompasses a therapeutic dose, and will provide the safety and tolerability underpinnings for the clinical drug development plan for LY3819253.

Up to 4 cohorts will be enrolled to characterize the dose response of LY3819253 on safety, tolerability, PK and PD markers. The first 3 cohorts will explore the efficacious dose range (2 doses) and 1 supratherapeutic dose. The planned dose levels for LY3819253 are 700 mg, 2800 mg and 7000 mg.

Cohort 4 is optional and may be used to characterize the dose-response relationship for dose selection in subsequent studies. The dose for Cohort 4 may be evaluated at a lower or equal level to the maximum investigated dose but will not exceed 7000 mg.

The doses are determined based on these key variables:

- projected human PK of the mAb, including lung tissue distribution
- in vitro binding potency to the viral targets
- neutralization of virus cell entry and replication, and
- antibody-viral dynamic modeling and simulation.

The projected human half-life is expected to be approximately 19 days based on PK/PD modeling.

The starting dose of 700 mg is expected to have a sustained concentration above the *in vitro* IC90 of viral cell-entry neutralization for at least 28 days. The maximum dose of 7000 mg is selected due to uncertainty in model predicted PK concentrations, viral load reduction and consideration of infusion volume in participants.

The dose levels are fixed, not body weight based. Given the planned dose levels, the predicted impact of body weight on therapeutic response will be minimal.

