7. TREATMENTS

Cohort	Study Treatment Name*	Treatment order in TFL
All	Pooled placebo IV	1
1	700 mg LY3819253 IV	2
2	2800 mg LY3819253 IV	3
3	7000 mg LY3819253 IV	4
4 (optional)	TBD mg LY3819253 IV	5

The following is a list of the study treatment abbreviations that will be used in the TFLs.

Abbreviations: IV = intravenous; TBD = to be determined.

* Planned doses presented - the actual dose administered will be displayed in the TFLs.

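### The SAP's example code for dose proportionality evaluates 700 mg at 750 mg and codes the 7000-to-700 mg contrast as 0.970 instead of 1

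*SAP*

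**What the plan says.** SAP 10.3.2 regresses log-transformed Cmax and AUC(0-∞) on log dose and reports dose-normalised geometric mean ratios with 90% confidence intervals. It names the comparison that matters: "The estimated ratio of dose-normalized geometric means of PK parameters between the highest and lowest doses will be used to assess dose proportionality".

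The example code then gives one estimate per dose and one contrast. The lowest dose is coded as "estimate '700 mg' intercept 1 log_dose 2.87506126 / alpha=0.1 cl; /*Log of 700". The contrast is coded as "estimate '2800 mg - 250 mg' log_dose 0.97003679 / alpha=0.1 cl; /*Difference in", and its comment goes on to name 7000 and 700 as the two doses.

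The doses themselves are not in doubt. Protocol 4.3 states: "The planned dose levels for LY3819253 are 700 mg, 2800 mg and 7000 mg". SAP section 7 lists Cohort 1 as "700 mg LY3819253 IV" and Cohort 3 as "7000 mg LY3819253 IV".

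**The concern.** The constant given as the log of 700 is not the log of 700 in base 10 or in natural logs, although the constants for 2800 mg and 7000 mg are right in base 10. The high-to-low contrast has three definitions that disagree: its comment (7000 and 700), its coefficient (0.970) and its label (2800 mg and 250 mg). No 250 mg dose is planned.

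This contrast is the only one in the code that supplies the ratio on which the SAP rests its assessment of dose proportionality. The code would run without an error, and the comments vouch for the wrong values, so nothing would prompt a check. At stake are the reported 700 mg geometric mean, the 7000-to-700 ratio and their 90% confidence intervals, for both Cmax and AUC(0-∞).

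**Working it through.** **Inputs.** Doses of 700, 2800 and 7000 mg come from Protocol 4.3 and SAP section 7. The coded constants 2.87506126, 3.44715803, 3.84509804 and 0.97003679 come from SAP 10.3.2. The slopes b = 0.8, 1.0 and 1.2 are illustrative assumptions; b = 1 is exact proportionality.

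**Step 1: the constants.**

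| Coded as | Coded constant | Correct log10 | Coded constant corresponds to |
|---|---|---|---|
| 700 mg | 2.87506126 | 2.84509804 | 750 mg |
| 2800 mg | 3.44715803 | 3.44715803 | 2800 mg |
| 7000 mg | 3.84509804 | 3.84509804 | 7000 mg |

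The natural log of 700 is 6.5511, so the choice of base does not explain the first row.

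**Step 2: the contrast.**

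- Coefficient: 3.84509804 − 2.87506126 = 0.97003678, which matches the coded 0.97003679 apart from the last digit. This is log10(7000/750), so the wrong constant was carried forward. A misread digit in the PDF would not produce two figures that agree in this way.
- Comment: log10(7000/700) = 1.
- Label: log10(2800/250) = 1.0492.

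**Step 3: the 700 mg geometric mean.** With log_pk un-normalised, the estimate is inflated by the factor (750/700)^b, which is 1.0567, 1.0714 and 1.0863 at b = 0.8, 1.0 and 1.2. That is 5.7%, 7.1% and 8.6% too high.

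**Step 4: the 7000-to-700 ratio.** The code returns 10^(0.97003679 b); the correct value is 10^b. The dose-normalised ratio depends on a divisor that the code does not show, so both candidates are given.

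| Slope b | Ratio, coded | Ratio, correct | Coded ÷ 10 | Coded ÷ 9.333^* | Correct normalised |
|---|---|---|---|---|---|
| 0.8 | 5.971 | 6.310 | 0.597 (−5.4%) | 0.640 (+1.4%) | 0.631 |
| 1.0 | 9.333 | 10 | 0.933 (−6.7%) | 1.000 (0%) | 1.000 |
| 1.2 | 14.590 | 15.849 | 1.459 (−7.9%) | 1.563 (−1.4%) | 1.585 |

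^* The ratio obtained if the same wrong coefficient is used to normalise: 10^(0.97003679 (b − 1)).

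**Step 5: the confidence interval.** The contrast is the slope multiplied by its coefficient, so the estimate and its standard error are both scaled by 0.970. On the log scale the 90% interval is shifted and is 1 − 0.970 = 3.0% too narrow.

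**The case against.** The strongest reply is that this is labelled example code. The prose names the right model, comparison and confidence level, and the comments show the right intent. The stray 250 mg suggests code carried over from a template. Harm arises only if the block is run uncorrected. That stands, but the block holds constants specific to this study, and its comments affirm the wrong ones.

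Second, the code also outputs the fitted slope with its 90% interval, and the correct dose-normalised 7000-to-700 ratio is 10^(b − 1). The right answer can therefore be recovered from the same run. That is true, but it is a workaround. A programmer who uses the coded contrast gets the wrong figure.

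Third, log_pk is not defined in the code. If it had been dose-normalised before fitting, the slope would be b − 1. The 700 mg factor would then be (750/700)^(b − 1), or 0.986, 1.000 and 1.014 at b = 0.8, 1.0 and 1.2, and no 9.33-against-10 comparison would arise. The SAP's description of log-transformed Cmax and AUC(0-∞) in a power model makes un-normalised values the more natural reading. The point does mean that the size of the error rests on that reading.

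Finally, dose proportionality is not a listed endpoint and the SAP sets no acceptance limits for it. That stands and limits the severity.

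**Conclusion.** The code is wrong as written. The estimate labelled 700 mg is evaluated at 750 mg, the high-to-low coefficient is 0.970 where 1 is required, and the contrast label matches neither the coefficient nor the comment.

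For un-normalised log_pk, with everything in base 10, the 700 mg geometric mean is 7.1% too high at slope 1, the 7000-to-700 ratio is 9.33 instead of 10, and the interval for the contrast is 3.0% too narrow on the log scale. For the dose-normalised ratio, which is the SAP's stated measure, the error at slope 1 is −6.7% if the divisor is the true tenfold dose ratio and zero if the same wrong coefficient is used. The error is systematic and does not shrink with sample size.

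The fitted slope and its interval, the by-dose descriptive summaries and the Day 29 concentration endpoint are unaffected. The correction should be made before the code is used, but it does not touch the trial's main conclusions.

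**What to change.** In the SAP 10.3.2 example code:

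1. Set the 700 mg coefficient to 2.84509804.
2. Set the high-to-low coefficient to 1 and relabel the contrast as 7000 mg minus 700 mg.
3. State that log_dose and log_pk are both in base 10 and that log_pk is not dose-normalised. Then show the normalisation: subtract log10(highest/lowest) from the contrast estimate and from both confidence limits, and back-transform with 10^x. If log_pk is in fact normalised before fitting, say so and omit the subtraction, which would otherwise be applied twice.
4. Derive the constants from the doses actually given rather than typing them in. Protocol 4.3 says the optional Cohort 4 dose "may be evaluated at a lower or equal level to the maximum investigated dose but will not exceed 7000 mg", and SAP section 7 notes: "Planned doses presented - the actual dose administered will be displayed in the TFLs". If Cohort 4 adds a level below 700 mg, a fixed 7000-to-700 contrast would no longer compare the highest and lowest doses.

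The cost is two coefficients, one label and one added line. Data collection and all other analyses are unchanged.

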10.4 Pharmacodynamic Assessment

10.4.1 Pharmacodynamic Analysis

The PD endpoints for this study are:

- Change from baseline in SARS-CoV-2 viral load (Days 7, 11, 15 and 22)
- Viral load AUC (Day 1 to 29)
- Proportion of participants that achieve SARS-CoV-2 clearance (Days 7, 11, 15, 22)
- Time to SARS-CoV-2 clearance
- Viral resistance to LY3819253 (from baseline to Day 29)

Viral clearance is defined as two consecutive negative SARS-CoV-2 values from the nasopharyngeal swabs. When deriving clearance, any missing data from the nasopharyngeal swabs will be set to positive. Time to SARS-CoV-2 clearance is defined as the earliest timepoint of the two.

If these two negative values are followed by a subsequent positive value, this measurement will be flagged and considered for evaluation of viral mutation or resistance.

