Pharmacokinetic (PK) sample		X			X			X		X	Х	Х	Х	Day 1: before the infusion and anytime just prior to the end of infusion. All other scheduled samples may be taken at any time during that scheduled day. Lilly-designated laboratory

Study J2W-MC-PYAA	Screening		Doul	ble-bli	nd trea	atmen	t and a	issessr	nents		Discharge from hospital or	Follow-up if inpatient in hospital	Post- treatment follow-up	
Study Day		1	2	3	4	7	11	15	22	29	ED	Every 7 days until discharge or Day 60	60	
Visit window (± number of days)	-2						2	2	2	2	2	2	4	
Immunogenicity (ADA) sample		Х						Х		X	Х	Х	Х	Day 1: before the infusion. All other scheduled and unscheduled immunogenicity samples should be collected with a time-matched PK sample. Lilly-designated laboratory
Pharmacodynamic sample		X		х		X	Х	Х	X	X	Х	Х		SARS-Cov-2 swab Methods include nasopharygeal (preferred) or mid-turbinate. The same method of sample collection must be used per participant for the duration of the study. Switching methods is not allowed. Day 1: before the infusion. Lilly-designated laboratory
Exploratory biomarker samples		Х		Х		Х	Х	Х	Х	Х	Х	Х		Day 1: before the infusion Lilly-designated laboratory
Pharmacogenetics sample		Х												Lilly-designated laboratory
Randomization and D	osing													
Randomization		Х												
Administer study intervention (IV infusion)		Х												

Abbreviations: ACVPU = alert, consciousness, verbal, pain, unresponsive scale; ADA = anti-drug antibody; BP = blood pressure; CKD-EPI = Chronic Kidney DiseaseEpidemiology Collaboration equation; CRP = C-reactive protein; ECG = electrocardiogram; ECMO = extracorporeal membrane oxygenation; ED = early discontinuation; FiO2 = fraction of inspired oxygen in the air; ICU = intensive care unit; IV = intravenous; NSAIDS = non-steroidal anti-inflammatory drugs; SARS-Cov-2 = severe acute respiratory syndrome coronavirus 2; SpO2 = saturation of peripheral oxygen; WOCBP = women of child-bearing potential.

2. Introduction

The efficient community spread of SARS-CoV-2 has resulted in the current pandemic of COVID-19, which in severe and critical cases results in progressive pulmonary infection, complicated by respiratory failure, with a high prevalence of acute respiratory distress syndrome. Although several therapies have been explored in severe COVID-19, none have improved survival, including antivirals, glucocorticoids, and immunoglobulins (Liu et al 2020).

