8.6. Pharmacodynamics

The SARS-CoV-2 viral RNA level and viral clearance will be evaluated by either a nasopharyngeal swab or mid-turbinate swab at times specified in the SoA. The same method of sample collection must be used per participant for the duration of the study. Switching methods for a participant is not allowed.

The nasopharyngeal swab is the preferred method and will be taken from both nostrils. The nasopharyngeal procedure is described in Section 10.7.

Sample retention is described in Section 10.1.12. Remaining samples may be used for additional exploratory studies to better understand LY3819253 and the disease, which may include sequencing and/or culture of the virus for future studies.

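### The SAP derives viral clearance from nasopharyngeal swabs only, so valid results from the mid-turbinate swabs that the current protocol permits cannot establish clearance

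*SAP*

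**What the plan says.** **SAP 10.4.1 (Pharmacodynamic Analysis).** The definition reads: "Viral clearance is defined as two consecutive negative SARS-CoV-2 values from the nasopharyngeal swabs". The missing-data rule follows: when clearance is derived, "any missing data from the nasopharyngeal swabs will be set to positive". The time-to-event endpoint rests on the same pair of negatives: "Time to SARS-CoV-2 clearance is defined as the earliest timepoint of the two". The SAP does not mention mid-turbinate swabs anywhere.

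**Protocol 8.6 (Pharmacodynamics).** Here "viral clearance will be evaluated by either a nasopharyngeal swab or mid-turbinate swab at times specified in the SoA", and "Switching methods for a participant is not allowed". The Schedule of Activities agrees, in its comment on the pharmacodynamic sample: "Methods include nasopharygeal (preferred) or mid-turbinate".

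**Which version the SAP reflects.** SAP Section 3 says that the SAP was prepared from the original protocol and Amendment (a). The summary of changes at the front of the current protocol shows that the mid-turbinate method came in with the later amendment, after site feedback. SAP Section 12 declares no departures from the protocol's analyses.

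**Who is analysed.** SAP Section 9 limits the PD population to treated participants with at least one post-baseline value for the endpoint in question. SAP 10.1 says that summaries and analyses are generally confined to the relevant population.

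**The concern.** Both texts are current and they disagree on which swabs count. Because a participant stays with one method throughout, someone followed by mid-turbinate swab has no nasopharyngeal series in the study. The SAP definition therefore has nothing to work on for that participant, even if every swab taken was negative.

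Two endpoints depend on the rule. Time to clearance is a secondary endpoint, summarised by treatment and shown as a Kaplan-Meier plot. The proportion cleared at Days 7, 11, 15 and 22 is exploratory. It is tabulated and, if there are enough data, each dose is compared with pooled placebo by a chi-square test. At stake is whether valid results from a permitted method enter these analyses.

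**Working it through.** The plan gives no clearance rate, no power for clearance and no mid-turbinate share, so there is no figure to reproduce. The check has two parts: what the rule does to one participant, and what follows for the arm.

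**1. One participant.** The Schedule of Activities places PD swabs on Days 1, 3, 7, 11, 15, 22 and 29 (leaving aside discharge and later inpatient visits). Each result is negative, positive or missing, which gives 3^7 = 2187 patterns. Clearance needs two adjacent negatives, and a missing value counts as positive.

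- *Nasopharyngeal participant.* Let a(n) be the number of patterns of length n without two adjacent negatives. Then a(n) = 2a(n−1) + 2a(n−2), with a(1) = 3 and a(2) = 8. The sequence continues 22, 60, 164, 448, 1224. Patterns that count as cleared: 2187 − 1224 = 963.
- *Mid-turbinate participant, SAP text as written.* There are no nasopharyngeal results, so no pattern qualifies: 0 of 2187.
- *Mid-turbinate participant, own method used.* The same 963 of 2187 as for the nasopharyngeal participant.

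These are counts of patterns, not probabilities. They show that the outcome is fixed by the swab method and not by the results. The definition alone is enough for this, because two nasopharyngeal negatives can never be supplied. The missing-as-positive rule bears only on what happens next.

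**2. The arm.** Let q be the share followed by mid-turbinate swab (unknown) and p the true clearance proportion, assumed equal for both methods.

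*Reading A: absent nasopharyngeal results are set to positive and the participant stays in the denominator.* Reported proportion = (1 − q) × p.

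*Reading B: the participant has no measure for this endpoint and leaves the PD population.* Reported proportion = p, from a fraction (1 − q) of the participants. The standard error grows by 1/√(1 − q).

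| q (assumed) | Reading A, true p = 80% | Reading B, proportion | Reading B, standard error multiplied by |
|---|---|---|---|
| 10% | 0.90 × 80 = 72% | 80% | 1/√0.90 = 1.05 |
| 25% | 0.75 × 80 = 60% | 80% | 1/√0.75 = 1.15 |
| 50% | 0.50 × 80 = 40% | 80% | 1/√0.50 = 1.41 |

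If clearance differs by method, Reading B is no longer unbiased. The true proportion is (1 − q) × p_NP + q × p_MT, while the analysis reports p_NP. The error is q × (p_NP − p_MT).

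**3. Between arms.** Placebo is pooled over all cohorts (SAP Section 7), while each of the doses in Cohorts 1 to 3 comes from one sequential cohort. If use of the method changes between cohorts, q can differ between a dose arm and pooled placebo. As an illustration, assume true clearance of 70% in both arms, with q = 10% on placebo and 30% on active drug:

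- Reading A: 0.90 × 70 = 63% against 0.70 × 70 = 49%, an apparent deficit of 14 points where there is none.
- Reading B: 70% against 70%, with no false difference.

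**The case against.** **The population rule.** The strongest point is that SAP Section 9 admits only participants with a post-baseline value for the endpoint. If only nasopharyngeal results count, a mid-turbinate participant has provided none, and an imputed positive is hardly a value provided. On that reading the participant is dropped and not miscounted. This stands. A reader might infer from the missing-as-positive sentence that reported clearance must fall to (1 − q) of the truth; the documents do not settle that, so the 72%, 60% and 40% figures belong to one reading only. The objection does not restore the lost results, however. Under it, valid swabs are still discarded.

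**Nothing is missing.** The schedule has one PD swab per visit, taken by either method. For a mid-turbinate participant no nasopharyngeal swab was due, so none is missing. This is a fair reading of the imputation sentence, but the definition sentence still excludes the results.

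**Version lag.** A reader might infer that the sponsor chose to restrict clearance to nasopharyngeal swabs. The documents point the other way: the SAP rests on Amendment (a), and Section 12 declares no changes from the protocol. That explains the wording but does not change its effect.

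**Protocol 8.6 still applies.** The SAP supersedes only the protocol's statistical considerations, so a programmer could follow 8.6 and use whichever swab was taken. That would be sensible, but it would be an unwritten choice against the stated derivation, in a study where the sponsor is unblinded.

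**Size.** Nasopharyngeal sampling is the preferred method, so q may be small. All treatment comparisons are exploratory under protocol 9.1. This stands and limits the weight of the point.

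**Conclusion.** Wrong as written. The SAP's clearance rule does not match the current protocol, and a participant followed by the permitted mid-turbinate swab cannot meet it. That conclusion rests on the texts alone.

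The size is conditional. It depends on q, which the documents do not give, and on whether such participants are kept as non-clearers or dropped. If kept, the reported proportion is (1 − q) times the truth, assuming equal true clearance by method, and they contribute no event to the time-to-clearance analysis. If dropped, precision is lost, and bias arises only if method is related to outcome.

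A reader might go further and infer a false difference between arms. The documents do not support that as a finding: it needs Reading A with unequal method use between arms, or Reading B with a link between method and outcome that does not cancel between arms. Nothing in the documents shows either. Nor does the problem reach the primary safety endpoint. The viral-load change and AUC derivations in SAP 10.4.2 name no swab type, so they are untouched as well.

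**What to change.** In both sentences of SAP 10.4.1, the definition and the missing-data rule, replace the reference to nasopharyngeal swabs with: *the participant's scheduled SARS-CoV-2 PD swabs (nasopharyngeal or mid-turbinate, whichever method was used for that participant)*. Update SAP Section 3 to cite the current protocol amendment. A sensitivity summary of clearance by swab method would be a reasonable addition, but the correction does not depend on it.

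The cost is a wording change in two adjacent sentences. It needs no new data and no protocol amendment, and it should be made before clearance is derived. Mid-turbinate participants are then classified by the same rule as everyone else, and the choice between the two readings no longer arises.

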5.1. Inclusion Criteria

Participants are eligible to be included in the study only if all of the following criteria apply:

Age

1. Are ≥ 18 and ≤ 85 years of age at the time of randomization

Type of Participant and Disease Characteristics

- 2. In the judgement of the investigator, have moderate or severe COVID-19 illness per the FDA resource page (WWW) (Section 10.8, Appendix 8)
- 3. This criterion was removed
- 4. Are hospitalized, or in the process of being admitted to hospital, and have an initial laboratory determination of current COVID-19 infection ≤14 days of randomization.

Sex

- Are men or non-pregnant women Reproductive and Contraceptive agreements and guidance is provided in Section 10.4, Appendix 4.
- 6. Criterion 6 merged with criterion 5.

Study Procedures

- 7. Understand and agree to comply with planned study procedures
- 8. Agree to the collection of nasopharyngeal swabs and venous blood

Informed Consent

9. The participant or legally authorized representative give signed informed consent as described in Section 10.1.3, which includes compliance with the requirements and restrictions listed in the informed consent form (ICF) and in this protocol.

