9. DEFINITION OF ANALYSIS POPULATIONS

The "Entered" population will consist of all participants who sign the informed consent form.

The "Safety" population will consist of all participants randomly assigned and who received study intervention (either placebo or LY3819253). Participants will be analyzed according to the intervention they actually received.

The "Pharmacokinetic" population will consist of all randomized participants who received study intervention (LY3819253) and have at least one evaluable PK sample. Participants will be analyzed according to the intervention they actually received.

The "Pharmacodynamic" population will consist of all randomized participants who received study intervention (either placebo or LY3819253) and provided at least one post-baseline measure for the relevant endpoint. Participants will be analyzed according to the intervention they actually received.

All protocol deviations that occur during the study will be considered for their severity/impact and will be taken into consideration when participants are assigned to analysis populations.

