10.4.2 Pharmacodynamic Statistical Methodology

SARS-CoV-2 viral load

SARS-CoV-2 viral load will be measured using the cycle time (CT) from a polymerase chain reaction (PCR) assay. Higher CT values indicate a lower viral load.

SARS-CoV-2 viral load, including changes from baseline, will be summarized and plotted by treatment, and listed. Baseline is defined as the Day 1 predose assessment. Overlaying individual profiles of SARS-CoV-2 viral load data will also be presented graphically over time.

Changes from baseline in SARS-CoV-2 viral load data will be statistically analyzed using a mixed model for repeated measures (MMRM). The model will contain baseline as a covariate, treatment, day and treatment-by-day interaction as fixed effects, and subject as a random effect. The unstructured covariance matrix will be selected initially; if this analysis fails to converge another covariance structure will be selected based on AIC and BIC values. The least square (LS) means and treatment differences (LY3819253 minus pooled placebo at each dose level) will be calculated and presented with their corresponding 90% confidence intervals (CIs). All available data will be used in the analysis.

An example of the SAS code that will be used is as follows:

```
proc mixed data=xxx;
class trtmnt subject day;
model chg = base trtmnt day trtmnt*day / alpha=0.1 cl ddfm=kr2;
repeated day / subject=subject type=un;
lsmeans trtmnt*day / alpha=0.1 cl pdiff;
ods output lsmeans=lsm01 diffs=diff01;
run;
```

where chg is the change from baseline, base is the baseline in SARS-CoV-2 viral load data, day is the study day, and trtmnt is the treatment used in the comparison.

A Bayesian linear mixed effect model will be fitted to evaluate the critical success factor by Lilly statistics group with the model listed below:

 $y_{ijk} = \mu + \alpha \times base + \alpha_i + \beta_k + (\alpha\beta)_{ik} + \varepsilon_{ij} + \varepsilon_{ijk}$

Where y_{iik} : the change from baseline for treatment i, subject j at day k

μ: a constant common to all observations

 α : a fixed coefficient on the covariate baseline viral load

 $\alpha_{i:}$ a parameter corresponding to treatment i

 $\beta_{k:}$ a parameter corresponding to day k

 $(\alpha\beta)_{ik:}$ an interaction parameter corresponding to treatment i and day k

 ϵ_{ij} , ϵ_{ijk} : random error for between and within subject variability

prior μ , α , α_{i} , β_{k} , $(\alpha\beta)_{ik} \sim N(0, 100)$

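### SAP 10.4.1 lets swabs that were already negative before dosing count as viral clearance, which is expected to dilute the clearance comparison

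*SAP*

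**What the plan says.** The rule is in SAP 10.4.1: "Viral clearance is defined as two consecutive negative SARS-CoV-2 values from the nasopharyngeal swabs". The event is dated by the next part of the rule: "Time to SARS-CoV-2 clearance is defined as the earliest timepoint of the two". For deriving clearance, "any missing data from the nasopharyngeal swabs will be set to positive". Nothing there confines the pair to swabs taken after the infusion, and nothing requires a positive swab on Day 1.

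The swab series in Protocol 1.3 starts on Day 1 before the infusion and continues on Days 3, 7, 11, 15, 22 and 29, with further swabs at discharge and during prolonged hospital stay. For viral load, SAP 10.4.2 states: "Baseline is defined as the Day 1 predose assessment".

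On entry, Protocol 5.1 (criterion 4) asks that participants "have an initial laboratory determination of current COVID-19 infection ≤14 days of randomization". The pharmacodynamic population in SAP 9 takes everyone who was dosed and "provided at least one post-baseline measure for the relevant endpoint".

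Under SAP 10.4.2, the clearance proportion (Days 7, 11, 15 and 22) is tabulated and, if data suffice, tested by chi-square for each dose against pooled placebo. Logistic regression on treatment is optional. Time to clearance gets a summary and a Kaplan-Meier plot, with no test. The repeated-measures and AUC models for viral load include baseline viral load; the clearance analyses name no baseline viral term. Protocol 3 lists time to clearance as secondary and the clearance proportion as exploratory.

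**The concern.** A participant whose virus is already undetectable before the infusion cannot show an effect of the drug on clearance. The entry test may be up to 14 days old, so such participants can be enrolled. Sites cannot screen them out on the study swab, because Protocol 10.2 has it assayed at a sponsor-designated laboratory without returning results. The rule and the population together then allow such a participant to be counted as cleared on either treatment.

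Two effects need to be kept apart. The clearance proportion is affected because baseline-negative participants stay in the analysis. The Kaplan-Meier curve is affected in addition because the event is dated at the earlier swab, which can be the predose one. At stake is how readable the antiviral signal is in a small dose-finding study.

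**Working it through.** The documents give no clearance rate, sample size or alpha for these endpoints, so there is no stated figure to reproduce.

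**Step 1. Apply the rule literally.** Swab results on Days 1, 3, 7, 11, 15, 22, 29:

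| Pattern | Clearance day, rule as written | Clearance day if both swabs must be post-dose |
|---|---|---|
| − − − − − − − | Day 1 (predose) | Day 3 |
| − − + + − − − | Day 1 (predose) | Day 15 |
| − + − − − − − | Day 7 | Day 7 |
| − + + + + + + | none | none |
| + + − − − − − | Day 7 | Day 7 |

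Time-zero credit needs a negative Day 1 swab and a negative next swab. A missing Day 3 swab is set to positive and blocks it. In the second row, the later positive is only flagged for evaluation of mutation or resistance, although the first negative preceded any drug. The first row shows that a post-dose rule alone is not enough: the participant is still credited, only at Day 3.

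**Step 2. Dilution of the proportion.** Let f be the share of each arm credited because they were already negative, and pC and pT the clearance rates in everyone else. The observed rate is f + (1 − f)p, so the difference is (1 − f)(pT − pC). Assumed rates, not from the documents: pC = 30%, pT = 60%.

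| f | Placebo | Active | Difference |
|---|---|---|---|
| 0% | 30% | 60% | 30 points |
| 5% | 33.5% | 62% | 28.5 points |
| 10% | 37% | 64% | 27 points |
| 20% | 44% | 68% | 24 points |
| 30% | 51% | 72% | 21 points |

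The share f cannot exceed the baseline-negative share. If the percentages are read as baseline-negative shares, and uncredited baseline-negatives clear like everyone else, the differences are floors: the true dilution is this large or smaller.

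**Step 3. Arms of 6.** Cohorts 1–3 give 6 participants per dose and 3 × 2 = 6 pooled placebo. With baseline-negative share b, the chance of at least one such participant in an arm is 1 − (1 − b)^6 = 47%, 74% and 88% at b = 10, 20 and 30%. The chance that two arms of 6 differ by 2 or more such participants is 13%, 27% and 34%. If k of 6 are counted cleared, one of them already negative, removing that participant changes the rate by k/6 − (k − 1)/5 = (6 − k)/30: 17 points at k = 1, 10 at k = 3, 0 at k = 6.

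**Step 4. Kaplan-Meier.** If f are dated at time zero, each curve starts with a step of f. With assumed exponential medians of 10 and 7 days in the rest, the arm median is the original median × log2[2(1 − f)]. The gap between arms falls from 3.0 days to 2.5, 2.0 and 1.5 days at f = 10, 20 and 30%.

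**Step 5. Power if Cohort 4 is filled.** Up to 50 + 6 = 56 pooled placebo against 50 on the Cohort 4 dose (assuming that dose is analysed separately), pooled-variance normal approximation, assumed two-sided 0.05, 30% versus 60%, and every baseline-negative credited:

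| f | All participants | Baseline-positive only |
|---|---|---|
| 0% | 88.4% | 88.4% |
| 10% | 80.2% | 84.8% |
| 20% | 70.5% | 80.3% |
| 30% | 60.2% | 74.7% |

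This is the best case for restricting. If 20% were baseline-negative but none were credited and all cleared like the rest, the full set would keep 88.4% and the restricted set would have 80.3%.

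**The case against.** The SAP never says that the Day 1 swab may be one of the two negatives. Clearance is tabulated only at post-dose days, SAP 9 asks for a post-baseline measure, and achieving clearance can naturally be read as something that happens after dosing. The table shells mentioned in SAP 3 are not available here and may settle it. This stands as a limit: that Day 1 counts is inferred from the absence of any restriction. It does not remove the point, because a post-dose reading still credits a participant negative on Days 1, 3 and 7.

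A reader might infer more than the documents support:
- That every baseline-negative participant counts as a responder. A negative Day 1 followed by a positive Day 3 is not credited at time zero and may never be credited.
- That each such participant moves an arm of 6 by 17 points. That is the maximum.
- That the comparison is always pulled toward no difference. This holds in expectation only.
- That these participants carry no information. Some Day 1 negatives may be false negatives with observable clearance later.

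The stakes are also limited. Protocol 9.1 makes all tests exploratory, the viral-load models adjust for baseline, and listings and individual profiles will show who was negative on Day 1.

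**Conclusion.** The point holds in limited form. As written, the clearance rule and the analysis population can count pre-dose negatives as cleared, and no other provision in the two documents prevents it. The expected difference in clearance proportion becomes (1 − f)(pT − pC), and Kaplan-Meier curves can start with a step at time zero.

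The size rests on assumptions. Neither f nor the 30% and 60% rates are in the documents, and the 14-day window is an outer limit that says nothing about how many participants are negative on Day 1. It would be wrong to conclude that the bias is of known size or certain direction in the 6-participant arms. The effect is confined to one secondary endpoint without a formal test and one exploratory endpoint with a conditional chi-square test. The primary safety objective is not affected. The SAP should be corrected before the clearance data are analysed.

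**What to change.** In SAP 10.4.1:
- Analyse clearance proportion and time to clearance in participants with an observed positive Day 1 predose pharmacodynamic swab.
- Require both negative swabs to be post-infusion. Both conditions are needed, as Step 1 shows.
- State that a missing Day 1 swab is not treated as positive for this purpose; otherwise the missing-data rule would admit the participant.
- List baseline-negative participants separately by arm.
- Keep the all-participant analysis as a sensitivity analysis.

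The restriction uses a swab taken before the infusion, so treatment cannot influence who is included. The change is SAP wording only, with no new visit or sample. Because Protocol 9.5 provides for unblinded pharmacodynamic reviews during the study, the change should be dated and its reason recorded.

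The cost is fewer participants in the clearance analyses: about 2 of 6 per arm if 30% are baseline-negative (0.3 × 6 = 1.8), including some whose Day 1 negative may have been false. The sensitivity analysis covers that loss.
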